**Analysis F. Cox proportional hazard modelling.**

For participants with the CNV subtype only an exploratory analysis of the hazard ratio for the covariate “percentage of classic” to explore association between the occult/classic mix and conversion.

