# **3.1.** Definition of the study eye

The "study eye" is the eye without nAMD at the baseline visit.

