## **Eligibility**

Patients with newly diagnosed nAMD in one eye and an unaffected second eye (study eye).

Inclusion criteria:

- Newly diagnosed nAMD in one eye and an unaffected second eye (diagnostic FFA to be within 6 weeks prior to consent)
- About to commence or recently commenced anti VEGF therapy in the first eye
- Age 50 -95

Exclusion criteria:

- patients with a history of nAMD in both eyes;
- nAMD in study eye detected at baseline;
- presenting visual acuity worse than 68 letters;
- retinal pathology in the study eye which can confound subsequent assessments (e.g. diabetic retinopathy, macular hole);
- not undergoing regular monitoring in standard of care;
- patients who cannot give informed consent;
- unable to undergo a fundus fluorescein angiography (FFA) test;
- patients whose baseline FFA was more than 6 weeks ago

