## **Analysis**

- **Analysis objectives**

1. Determine the diagnostic monitoring performance of the interventions (ETDRS visual acuity; fundus evaluation of signs of nAMD; the Amsler test; clinical assessment of images captured by OCT; patient's subjective assessment of vision) against the reference standard of fundus fluorescein angiography.
2. Develop a risk prediction model using baseline characteristics to predict the development of nAMD in the study eye
3. Quantify the time to diagnosis and risk of conversion
4. Explore the impact of CNV subtype on time to conversion

- **Method**

Participants are categorised as nAMD or not nAMD according to the presence of a positive FFA result (as assessed by the responsible ophthalmologist) during the follow-up period. To address the analysis objectives, the following analyses are planned:

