**Analysis Objective 3: Quantify the time to and risk of conversion**

**Analysis E. time-to-conversion distribution.** The survival distribution of conversion to nAMD (defined as local FFA conversion in a first analysis; and as the clinical diagnosis in a second analysis) over the follow-up period will also be estimated. Participants that did not convert will be censored at the time of their last available observation. First, a Kaplan-Meier curve will be fitted to estimate the underlying nAMD conversion distribution. Second, time of conversion will be estimated based upon the date of conversion confirmation. The distribution will be estimated

assuming parametric distributions and addressing the interval nature of the data. This will be done using the *stintreg* command in Stata. Exponential, Weibull and log-normal proportional hazard survival models will be fitted. Furthermore, using an accelerated time failure approach, a generalised gamma distribution will also be used. Related assessments of fit will be summarised.

**Analysis Objective 4:** To explore the impact of CNV subtype on time to conversion

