### **Subgroup analyses**

We will undertake pre-planned subgroups evaluation according to type of AMD in the study eye (choroidal neovascularization (CNV) and Retinal angiomatous proliferation (RAP)) and concerning analysis A1. These subgroup analyses will be classified as exploratory and evaluated at the 2-sided 5% significance level. They will only be carried out on index test results status collapsed over the follow-up period with the local FFA as the reference standard following analysis 1. No formal paired comparisons will be carried out and the individual group sensitivity (with 95% CIs) will be calculated.

For participants with a CNV subgroup (in the -study eye) the proportion of classic will be quantified.

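### Analysis F does not say in which eye, or when, percentage classic is measured; on the reading the SAP best supports, only converters can enter the Cox model, so its hazard ratio cannot show association with conversion

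*SAP*

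**What the plan says.** The fourth analysis objective in the SAP is: "Explore the impact of CNV subtype on time to conversion". Analysis F is the only analysis that serves it, and its content is one sentence: "For participants with the CNV subtype only an exploratory analysis of the hazard ratio for the covariate “percentage of classic", with the aim "to explore association between the occult/classic mix and conversion". The sentence does not say which eye carries the CNV, when the percentage is measured, or what happens to participants who never convert.

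One other place in the SAP mentions this quantity. Subgroup analyses defines its groups as "subgroups evaluation according to type of AMD in the study eye (choroidal neovascularization (CNV) and Retinal angiomatous proliferation (RAP" and adds: "For participants with a CNV subgroup (in the -study eye) the proportion of classic will be quantified".

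The study eye starts without disease. Protocol section 3.1 says: "The 'study eye' is the eye without nAMD at the baseline visit". The SAP Eligibility section lists "nAMD in study eye detected at baseline" as an exclusion.

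For the first-affected eye, protocol section 8 counts type and severity of nAMD among the risk factors collected at baseline. SAP Appendix 1 lists that eye's type (CNV or RAP only) and its severity. Percentage classic is not in the appendix.

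**The concern.** A Cox model for time to conversion needs covariate values for everyone at risk, including those who do not convert. Percentage classic in the study eye cannot meet that need. It is read from an angiogram showing CNV, so it exists only once the eye has converted. A model using it conditions on the outcome: non-converters have no value and drop out, and everyone left is an event.

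At stake is the whole of analysis objective 4. A hazard ratio close to 1 from such a model could be reported as no effect of lesion subtype on conversion when the model had no means of detecting one.

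**Working it through.** **1. When the covariate exists, on the study-eye reading.**
- Protocol section 3.3 defines classic and occult CNV by the pattern of fluorescence on FFA.
- SAP Time points of outcome collection has the nAMD classification recorded at the FFA that settles whether nAMD is present.
- SAP Sensitivity analyses takes the date of the confirming FFA as the default event date.

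Measurement and event therefore coincide, and no participant has a value before the event.

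**2. The plan's own figures.** The inputs are in SAP Sample size: sensitivity 80% against 65%, disagreement 0.30, two-sided 5%, 90% power, 28% cumulative incidence at 3 years.
- Converters needed = [1.960 × √0.30 + 1.282 × √(0.30 − 0.15²)]² / 0.15² = (1.0735 + 0.6751)² / 0.0225 = 135.9, so 136.
- Participants = 136 / 0.28 = 486, against 491 stated.
- Expected conversions = 491 × 0.28 = 137, against over 130 stated.

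The plan's numbers reproduce closely. Analysis F has no sample size or event count of its own.

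**3. Who can enter on the study-eye reading.** Converters number about 137, and 491 − 137 = 354 non-converters (72%) have no covariate. Those converters whose lesion is not CNV drop out as well, so 137 is an upper figure. Every participant analysed is an event.

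**4. What the hazard ratio then measures.** Assume constant hazards λ₁ and λ₀ for two lesion types, with total λ = −ln(1 − 0.28)/3 = 0.1095 per year.
- Density of converting at time t with type k: λₖ·exp(−λt).
- Probability of converting with type k by 3 years: (λₖ/λ)·0.28.
- Density of t among converters of type k: λ·exp(−λt)/0.28.

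λₖ cancels. Conversion times have the same distribution for both types, so the hazard ratio among converters is 1 whatever the ratio λ₁/λ₀. Simulation with 491 participants agrees:

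| Incidence ratio, classic to occult | Mean hazard ratio, converters only |
|---|---|
| 0.25 | 1.03 |
| 0.5 | 1.01 |
| 1 | 1.00 |
| 4 | 0.99 |

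**5. If the hazards differ in shape.** Give both types the same 3-year cumulative hazard (28% conversion overall), one with Weibull shape 1.5 or 2 and the other with shape 1. The converter-only hazard ratio becomes about 0.74 to 0.77 and 0.62 to 0.64 respectively, with median conversion times of about 1.8 against 1.4 years and 2.0 against 1.4 years. The ratio moves because timing differs, although the two types have equal cumulative hazards.

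**6. The first-eye baseline reading.** Take a covariate known at entry, uniform from 0 to 100%, with non-converters censored at 3 years:

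| True hazard ratio, 0 to 100% classic | All participants | Converters only |
|---|---|---|
| 1 | 1.00 | 0.99 |
| 2 | 1.91 | 1.07 |
| 3 | 3.02 | 1.09 |

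The model works when everyone at risk is in it. Restricting even a valid baseline covariate to converters removes nearly all of the association.

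**The case against.** The strongest reply is that Analysis F never says study eye. The sentence under Subgroup analyses belongs to the accuracy analysis by lesion type, promises only a summary, and does not mention Analysis F. A sound reading is available: type and severity in the first eye are collected at baseline, Appendix 1 uses the CNV label for that eye, baseline FFA images go to the reading centre for grading, and Analysis E, just before, censors non-converters. A hazard ratio for conversion fits that design naturally. This stands in part. A reader might infer that the SAP commits itself to a study-eye covariate and so to an invalid model, and the text does not go that far. But the first-eye reading is not written down either, and where the SAP means the first-affected eye in Appendix 1 it labels it so. The protocol does not settle the matter, because this objective is not among those it lists.

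A second reply is that the objective, "To explore the impact of CNV subtype on time to conversion", asks about time, and a converter-only model can say something about time. That also stands. A reader might conclude that the hazard ratio would be wholly uninformative, but the differing-shape results in step 5 contradict this. The near-1 values in step 4 follow from assuming constant hazards. What remains is that a comparison of timing among converters does not answer Analysis F's own stated aim, which is association with conversion.

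A third reply is that this is one exploratory sentence outside the primary and secondary outcomes. That is correct and limits the weight of the point.

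**Conclusion.** The point holds conditionally. Analysis F leaves the eye, the time of measurement and the handling of non-converters undefined. On the reading the SAP text best supports, the model would contain at most about 137 converters, all of them events, and none of the roughly 354 non-converters. Its hazard ratio would reflect timing among converters and could sit near 1.0 despite a fourfold difference in how often the two lesion types arise.

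The counts rest on the plan's 491 participants and 28% incidence. The near-1 result rests on constant hazards and a two-category lesion type, whereas the SAP's covariate is a percentage. With other hazard shapes the ratio departs from 1 but still concerns timing only. On a first-eye baseline reading the Cox model is valid.

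Nothing in the documents carries Analysis F into the accuracy comparisons, the risk prediction model or the economic model, so a reader should not infer that any of those is compromised. This is a minor finding confined to one exploratory objective.

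**What to change.** State in Analysis F that the covariate is percentage classic in the first-affected (non-study) eye at the baseline FFA, that all participants with CNV in that eye are included, and that non-converters are censored as in Analysis E.

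Report study-eye percentage classic separately. Either describe it among converters, or estimate cause-specific hazards of conversion by lesion type over the whole cohort, so that non-converters contribute time at risk.

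The cost is mainly SAP wording. The drawback is that percentage classic in the first eye is not listed in Appendix 1 and the documents do not say that it is graded. It may have to be extracted from the baseline FFA images, which the protocol already has uploaded to and graded by the reading centre. If it cannot be obtained, drop the Cox hazard ratio and keep the descriptive or cause-specific version.

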**Missing data and indeterminate and unreliable results**

Absence of a positive reference standard during valid follow-up period will be presumed to indicate a negative result.

Indeterminate FFA results: As a default position indeterminate tests will be treated as missing, but there will be sensitivity analyses to test that assumption (see below). For the primary person level analysis (Analysis A1), if the last available reference standard is missing/indeterminate then the previous reference standard will be used. If no reference standards have been carried out after the baseline reference standard or they are all indeterminate/missing then that participant will be excluded from the analysis unless a curtailed period with a valid FFA and index test result exists.

For the prognostic model (Analysis D) the impact of missing covariate data will be assessed and multiple imputation will be used for baseline variables if considered appropriate.

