# 3.6.7. End of participant follow-up

All patients will be followed-up according to standard clinical practice up to 3 years from enrolment. Study monitoring follow-up will end prior to 3 years upon a clinical diagnosis of nAMD in the study eye or if a patient withdraws consent to continue this follow-up (see section 3.6.8 for information on the withdrawal procedures).

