#### **Reading centre**

An ophthalmic reading centre (Central Angiographic Resource Facility) located at Queen's University Belfast will independently undertake grading of anonymised images (FFA, OCT, fundus photography, autofluorescence- optional) acquired at all the timepoints highlighted in table 1.

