## **Statistical Principles**

### **Sample size**

The sample size is based upon comparative diagnostic accuracy to ensure the ability to detect differences in sensitivity and specificity between candidate tests. The calculation is based upon McNemar's test. (Obuchowski 1998) Under the primary analysis, a positive candidate test result will be defined as any positive result during the monitoring period on the respective test. At 2-sided 5% significance level and 90% power, a paired difference of 15% (80% to 65%) in sensitivity will require 491 participants (560 allowing for indeterminate/missing data results - including patients lost to follow-up cumulatively of up to 12%) given a cumulative incidence of 28% at 3 years. (Karnon 2008) This calculation assumes a disagreement between tests of 0.30 which was based upon data from a diagnostic study involving OCT for diagnosis glaucoma (HTA reference 09/22/111). A smaller difference in specificity will be identifiable (7%; 94% to 87% with power and significance levels as before) given most participants will not convert during the 3-year follow-up period even if the maximum level of disagreement occurs. The reference sensitivity and specificity values used in this calculation are the values observed for OCT in a pilot study with a similar study design. (Parnick-Silver 2012) Differences in sensitivity and specificity of at least 20% will also be detected at the same power and significance levels even if the sensitivities/specificity are substantially lower (e.g. 60 to 40%) or the level of missing data is higher (e.g. 20%). These calculations conservatively assume maximum possible disagreement between tests. A sample of this size would be of sufficient size for other measures of diagnostic performance (e.g. the sensitivity and specificity of individual technologies will be estimated to 95% confidence interval of width 16% and 10% respectively given a sensitivity/specificity of 65% or higher). Such a sample will also provide a sufficient sample for the GEE analysis given the anticipated gain in precision due to use of multiple repeated measures over

time. (Rochon 1998) Similarly, this sample will be more than sufficient for the development of a risk prediction model with over 130 events (conversions to AMD) anticipated and given 10 events per predictor variable/contract are typically recommended. (Peducci 1995).

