### **Participant inclusion criteria for analysis A**

For each of the 5 index tests, the following criteria will be applied separately:

1. Last FFA result shows no nAMD:

The participant will be included if there is **at least one prior** index test result during the follow-up period.

2. Last FFA result shows nAMD:

The participant will be included if there is an index test result within the previous 3-months. If a participant does not have an index test result within the previous 3-months of their last FFA the FFA will not be considered valid and we will look for an earlier FFA result for the participant and apply rules 1 and 2 again on the earlier FFA.

If no follow-up FFA is available which satisfies either criteria, then the participant will be excluded. If no follow-up FFA is available, the participant will be excluded from the analysis.

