**Table 2 Two by two table: definitions of test and disease status.**

	Index positive	Index negative
Reference standard positive: nAMD	True positives Any reference standard indicates nAMD in study eye AND Any index test result is positive during valid follow-up period	False negatives Any reference standard indicates nAMD in study eye AND Index test negative for all available prior time points
Reference standard negative: No nAMD	False positives All reference standard results indicate no nAMD in study eye AND Any positive index test result during valid follow-up period	True negatives All reference standard results indicate no nAMD in study eye AND Index test negative for all available prior time points

Sensitivity and specificity will be calculated with 95% confidence intervals calculated using the Agresti-Coull method (Zhou 2002). Positive and negative likelihood ratios will also be calculated with 95% confidence intervals calculated using the method in Zhou 2002. Diagnostic odds ratios and the proportion of indeterminate tests will be calculated with 95% confidence intervals. A ROC curve will be plotted and the area under the ROC curve calculated using the trapezoidal rule for visual acuity tests. The standard error for the AUC will be calculated using the method of DeLong, DeLong and Clarke-Pearson (1998) and used to form an asymptotic normal 95% confidence interval.

Monitoring sensitivity and specificity of the tests will be compared using McNemar's statistical test (with 95% confidence intervals produced using Newcombe's method) (Newcombe 1998).

For comparing sensitivities under the primary analysis, the McNemar 2x2 table will be constructed using only patients who have had a positive FFA result. They will be classified as having a positive index test, if the index test has any positive results during the valid follow-up period. They will be classified as having a negative index test, if all prior available tests have been negative during their valid follow-up period. For comparing specificities under the primary analysis, the McNemar 2x2 table will be constructed using only patients who have had negative FFA results throughout using the same index test classification.

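### In A1, eyes that exit on a clinical nAMD diagnosis with an indeterminate or absent local FFA drop out of the sensitivity denominator, and the planned safeguards cover this only in part

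*SAP*

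**What the plan says.** Protocol section 3.6.7 sets the early exit: "Study monitoring follow-up will end prior to 3 years upon a clinical diagnosis of nAMD in the study eye". Section 3.6.6 has the clinical diagnosis made after the triggered FFA, so the diagnosis, not the FFA reading alone, ends monitoring.

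The SAP defines disease in A1 by the local FFA only. Its section on missing and indeterminate results treats an indeterminate FFA as missing by default and adds, for A1, that "if the last available reference standard is missing/indeterminate then the previous reference standard will be used". If every post-baseline FFA is missing or indeterminate, the participant is excluded. The inclusion criteria for analysis A say the same: "If no follow-up FFA is available, the participant will be excluded from the analysis". The valid follow-up period ends at the last valid FFA. The McNemar table for sensitivity uses only participants with a positive FFA.

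The SAP expects such exits. Its dummy table of local FFA status at exit has clinical diagnosis as one of the reasons for a missing result.

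Three provisions bear on the problem:
- A7 counts a clinical diagnosis as disease.
- A4 to A6 use the reading-centre FFA.
- Sensitivity analyses 5 and 6 recode indeterminate results as positive or negative, but only if at least 10% are indeterminate.

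**The concern.** An indeterminate FFA in an eye that stays under monitoring normally does no harm, because a later FFA supersedes it. The rule bites when the indeterminate or absent FFA is the last one. Before 3 years, one way this arises is that the clinician diagnosed nAMD and monitoring stopped. Such eyes are probable converters, and A1 handles them in one of two ways:
- **Earlier follow-up FFA available.** It will normally be negative, since a positive one would usually have ended monitoring. The eye enters the no-nAMD row, and index results after that FFA, including those at the conversion visit, are discarded.
- **No earlier follow-up FFA.** The participant is excluded.

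So the set on which sensitivity is estimated is selected partly on the outcome, and each test's sensitivity and the paired differences then describe converters with a locally conclusive FFA. The 12% allowance in the sample size can make up lost numbers but not selective loss.

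**Working it through.** **The plan's own figure.** From the SAP, Sample size: "At 2-sided 5% significance level and 90% power, a paired difference of 15% (80% to 65%) in sensitivity will require 491 participants"; "This calculation assumes a disagreement between tests of 0.30"; "given a cumulative incidence of 28% at 3 years". With discordance ψ = 0.30 and d = 0.15, the McNemar formula is

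n = [1.960√ψ + 1.282√(ψ − d²)]² / d² = 135.9, so 136 converters, and 136/0.28 = 486 participants.

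This is within 3% of 491, and 491/0.88 = 558, about 560. With 491 × 0.28 = 137.5 converters, power is 90.3%. The plan's figures reproduce.

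**Effect of the A1 rule.** Two quantities are needed and neither is in the documents:
- f, the share of converters that exit on a clinical diagnosis with an indeterminate or absent local FFA;
- the index results in those eyes.

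For illustration, assume every lost eye is OCT-positive and let p be the comparator's positive rate among them. The planned discordant cells are 0.225 (OCT only) and 0.075 (comparator only). After the loss:
- OCT sensitivity = (0.80 − f)/(1 − f)
- comparator sensitivity = (0.65 − fp)/(1 − f)
- discordant cells = [0.225 − f(1 − p)]/(1 − f) and 0.075/(1 − f)
- power = Φ{[d√m − 1.960√ψ]/√(ψ − d²)}, where d and ψ are the difference and sum of those cells and m is the number of converters left.

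At f = 10%, observed OCT sensitivity is 0.70/0.90 = 77.8%. Power is shown for m = 137.5 × 0.90 = 123.7, and for m = 560 × 0.28 × 0.90 = 141.1, which applies if these losses are the only draw on the 12% allowance.

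| p | Comparator sensitivity | Difference (points) | Power, m = 123.7 | Power, m = 141.1 |
|---|---|---|---|---|
| 40% | 67.8% | 10.0 | 58% | 64% |
| 65% | 65.0% | 12.8 | 75% | 81% |
| 85% | 62.8% | 15.0 | 85% | 90% |
| 100% | 61.1% | 16.7 | 90% | 94% |

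The difference is unchanged when [0.15 − f(1 − p)]/(1 − f) = 0.15, that is, at p = 85% for any f. Below that it shrinks; above it, it grows. If the lost eyes resemble the retained ones, it stays at 15 points and only numbers fall (power 87% at m = 123.7). If all lost eyes were OCT-negative, OCT sensitivity would rise to 0.80/0.90 = 88.9%.

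**Reach of the safeguards.**
- *Sensitivity analyses 5 and 6.* The base of the 10% trigger is not stated. If it is participants, 10% of 491 is 49.1, so up to 49 indeterminate results would leave both analyses unrun. That number equals 49/137.5 = 36% of expected converters, although not all would be converters. Neither analysis covers an FFA that was not done, and both recode all indeterminate results, not only those at a clinical exit.
- *A7.* It falls under the inclusion criteria headed for analysis A, which exclude anyone without a follow-up FFA. Yet reference definition C provides for an FFA not done. A7 also uses valid index results, and the valid period ends at the last valid FFA. Read literally, a test that was positive only at the conversion visit becomes a false negative in A7.
- *A4.* It changes the reference for every participant, so a difference from A1 cannot be attributed to these exits.

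**The case against.** The strongest reply is that the FFA-only reference in A1 is deliberate. The SAP states that an eye with a negative local FFA and a clinical exit is classed as no nAMD in A1 to A3, and gives the clinical standard its own analysis, A7. OCT and fundus evaluation are index tests, and the clinical diagnosis rests partly on them. Counting it as disease would build those tests into the reference and flatter them. This stands. It is why the local FFA should remain the A1 reference, and why the negative-FFA case, an explicit choice, is outside this point.

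Three stronger readings are tempting, and the documents do not support them:
- *All clinically diagnosed eyes are lost.* They are not. A diagnosis with a positive local FFA stays in the denominator, subject to the 3-month index-test rule.
- *Every use of the fallback is driven by the outcome.* Death, withdrawal and a missed or indeterminate FFA at 3 years trigger it too. Only the clinical exits are tied to the outcome.
- *The fallback contradicts Table 2*, where a reference negative requires that "All reference standard results indicate no nAMD in study eye". Because an indeterminate FFA counts as missing and lies after the last valid FFA, it is arguably not a result within the valid period. The conflict is weak.

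The reply that A7 and sensitivity analyses 5 and 6 already deal with the matter stands only in part, for the reasons worked through above.

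**Conclusion.** The concern holds for one defined group: eyes that exit on a clinical nAMD diagnosis with an indeterminate or absent local FFA. A1 removes them from the sensitivity denominator, and no planned analysis is certain to show what that does.

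A reader might infer that the rule biases A1 against OCT and shrinks its advantage. The documents do not support a direction. At f = 10% with all lost eyes OCT-positive, the 15-point difference can fall to 12.8, stay at 15.0 or rise to 16.7 as p goes from 65% to 85% to 100%. A high p is plausible for fundus evaluation, a lower one for the functional tests, so the ten planned comparisons may move in different ways. All of this rests on assumed f and p. If f proves close to zero, the effect is negligible, but the plan should make that visible. The change is worth making before analysis; it does not undermine the design.

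**What to change.** Keep the local FFA as the A1 reference and amend the SAP as follows.

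1. **A1 classification.** Do not place a participant who exited on a clinical nAMD diagnosis with an indeterminate or absent FFA in the no-nAMD row on an older FFA. List these exits separately and report their number, split into indeterminate and not done. The dummy table of FFA status at exit already gives part of this.
2. **Bounds, whatever the 10% trigger.** Report each test's sensitivity and the paired differences with these exits counted as nAMD, using index results up to the exit visit. Add a sensitivity analysis that uses the reading-centre grade of an indeterminate exit FFA. The reading centre "will independently undertake grading of anonymised images", and images from triggered FFAs are already uploaded under Protocol Table 1.
3. **A7.** Amend the inclusion criteria and the valid follow-up definition so that participants without a valid FFA are included and follow-up runs to the date of clinical diagnosis. This reconciles them with reference definition C.

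The cost is SAP wording and a little extra analysis, with no new data or procedures and no change to clinical management. Because a clinical diagnosis partly reflects OCT and fundus findings, the bound must be labelled as favouring those two tests.
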